4.5. Other Analyses

4.5.1. Subgroup analyses

4.5.1.1. Immunogenicity analysis

Subgroup analyses of the secondary immunogenicity endpoints will be made to assess consistency of the intervention effect across the following subgroups:

• Age group: 50-59 YOA, 60-69 YOA, ≥ 60 YOA, ≥ 70 YOA, ≥ 80 YOA

If the number of participants is too small (less than [10%]) within a subgroup, then the subgroup categories may be redefined prior to first analysis.

4.5.1.2. Safety analysis

Subgroup analyses of the secondary safety endpoints will be made to assess consistency of the safety profile across the following subgroups:

• Age group: 50-59 YOA, 60-69 YOA, $\ge 60 \text{ YOA}$, $\ge 70 \text{ YOA}$, $\ge 80 \text{ YOA}$

Specifically, the following safety analysis will be generated:

- The number and percentage of participants reporting each individual solicited administration site AE (any grade, Grade 3 and resulting in medically attended visit) and solicited systemic AE (any grade, Grade 3 and resulting in medically attended visit) during the 4-day follow-up period (i.e., the day of vaccination and 6 subsequent days) will be tabulated for each group after each dose and overall.
- The number and percentage of participants with any unsolicited AEs during the 30-day follow-up period (i.e., the day of vaccination and 29 subsequent days) with its exact 95% CI will be tabulated by group and by MedDRA Primary SOC, HLT and PTs

 For clinicaltrials.gov and EudraCT posting purposes, percentage of participants of combined solicited and unsolicited non-serious adverse events during the 30-day follow-up period (i.e., the day of vaccination and 29 subsequent days) will be produced by System Organ Class and preferred terms and according to occurrence of each event.

If the number of participants is too small (less than [10%]) within a subgroup, then the subgroup categories may be redefined prior to first analysis.

4.6. Interim Analyses

No interim analysis will be performed.

4.6.1. Sequence of analyses

The analyses will be performed stepwise:

- A first analysis will be performed on all immunogenicity, reactogenicity and safety data as clean as possible, when data are available for primary and secondary endpoints up to and including Visit 3 (Day 61) for all participants. This analysis will be considered as final for those endpoints.
- An end of study (EoS) analysis will be performed when all data up to the contact 6 months post-last dose will be available for all participants.
 - In the event of a delay in data availability for the first analysis, the first analysis and the end of study (EoS) analysis may be combined and performed concurrently.

4.7. Changes to Protocol Defined Analyses

In the protocol amendment 4 section 9.4.1: the possibility of performing a combined first and end of study (EoS) analysis if the data for the first analysis are not immediately available

5. SAMPLE SIZE DETERMINATION

Table 3 shows that the probability (global power) to reach the non-inferiority criterion with 722 evaluable participants (361 in Co-Ad and 361 in Control group) is at least 90.1%, with a 1-sided alpha = 0.025.

Table 3 Power to demonstrate non-inferiority of the Co-Ad group compared to the Control group in terms of GMT with 361 evaluable participants per group.

Endpoint	Standard deviation of log10 concentration	Reference ratio	Non inferiority margin	Type II error	Power
RSVPreF3 OA investig	ational vaccine No	n-inferiority* (1-sided test w	rith alpha = 2	.5%)
GMT RSV-A neutralization titers	0.45	1.05	1.5	0.4%	99.6%
GMT RSV-B neutralization titers	0.45	1.05	1.5	0.4%	99.6%
COVID-19 mRNA vacci	COVID-19 mRNA vaccine Non-inferiority* (1-sided test with alpha=2.5%)				
GMT SARS-CoV-2 neutralization titer	0.63	1.05	1.5	9.1%	90.9%
Global Power and Global Type II error				9.9%	90.1%

GMT: geometric mean titer

Non-inferiority limit = 0.176 (= $log_{10}[1.5]$).

Reference Ratio = $0.0212 = (-\log_{10}[1.05])$

Pass 2022 (Non-Inferiority test of 2 independent means). Power = 100-the Type II error (Beta). The Type II error (Beta) has been adjusted using Bonferroni's method (overall Type II error = sum of the individual Type II errors).

The primary objective analysis will be performed on the PPS. Assuming about 13% non-evaluable rate among enrolled participants up to 2-month post-vaccination (participants dropped-out or excluded from the PPS), a total of 830 participants (415 per group) will have to be vaccinated in order to reach 361 participants evaluable for the primary objective.

6. SUPPORTING DOCUMENTATION

6.1. Appendix 1 Study Population Analyses

6.1.1. Participant Disposition

A summary of the number and percentage of participants who completed the study as well as those who prematurely withdrew from the study will be provided. Reasons for study withdrawal will be summarized. For those who have neither completed nor withdrawn, they will be categorized as on study intervention or in follow up.

A summary of study intervention status will be provided. This display will show the number and percentage of participants who have completed the scheduled study intervention, are ongoing with study intervention, or have discontinued study intervention prematurely, as well as primary reasons for discontinuation of study intervention.

Those analysis will be based on the Screened set, Enrolled set, ES.

6.1.2. Demographic and Baseline Characteristics

Demographic and baseline characteristics (age at vaccination in years, sex, race, ethnicity, country) will be summarized by group using descriptive statistics, as described in Section 4.1.1. This analysis will be based on all analysis sets.

The following age categories will be considered in the analysis: 50-59 YOA, 60-69 YOA, \geq 60 YOA, \geq 70 YOA, \geq 80 YOA. In addition, for web posting purposes: 18-64 YOA, 65-84 YOA and >85 YOA.

If the summary of demographics meets the criteria for de-identification, as described in the relevant procedural document, a de-identified version should be produced.

Past medical conditions and current medical conditions as of screening will be summarized respectively and grouped by SOC, HLT and PT. This analysis will be based on ES.

6.1.3. Protocol Deviations

Important protocol deviations will be summarized.

Protocol deviations will be tracked by the study team throughout the conduct of the study. These protocol deviations will be reviewed to identify those considered as important as follows:

- Data will be reviewed prior to freezing the database to ensure all important deviations (where possible without knowing the study intervention details) are captured and categorised in the protocol deviations dataset.
- This dataset will be the basis for the summaries of important protocol deviations.

Protocol deviations which result in exclusion from the analysis set will also be summarized.

 Data will be reviewed prior to freezing the database to ensure all deviations leading to analysis population exclusions are captured and categorised in the protocol deviations ADaM dataset (note these exclusions are not captured in the SDTM dataset).]

A summary of important protocol deviations leading to exclusions from any analysis set will be provided by group, based on the Screened Set.

The number of participants screened for the study as well as the number of participants excluded from the Enrolled set, ES and the PPS analyses will be tabulated. These will be based on the Screened set, Enrolled Set and the ES, respectively.

6.1.4. Concomitant Medications

Concomitant medications will be coded using both the GSK Drug and WHO Drug dictionaries. However, the summary will be based on GSK Drug dictionary only. The summary of concomitant medications will be provided by ingredient, i.e. multi-ingredient medications will be summarized for each individual ingredient rather than a combination of ingredients. The summary will be created using ingredient base names, i.e. ingredients with the same base name but different salt will appear under one base name in the summary. Anatomical Therapeutic Chemical (ATC) classifications will not appear in the summary.

The number and percentage of participants using concomitant medication (any medication, any antipyretic and any antipyretic taken prophylactically) during the 4-day and the 30-day follow-up period after vaccination will be tabulated with exact 95% CI per group, after each vaccine dose and overall. The analysis will be performed on ES.

See Section 6.3.5 for handling of partial dates for medications, in the case where it is not possible to define a medication as prior or concomitant, the medication will be classified by the worst case, i.e., concomitant.

6.1.5. Concomitant Vaccinations

The number and percentage of participants and doses with concomitant vaccination during the 30-day follow-up period (i.e., on the day of vaccination and 29 subsequent days) will be tabulated with exact 95% CI per study group, after each vaccine dose and overall. The analysis will be performed on ES.

See Section 6.3.5 for handling of partial dates for vaccinations, in the case where it is not possible to define a vaccination as prior or concomitant, the vaccination will be classified by the worst case, i.e., concomitant.

6.1.6. Study Intervention Compliance

Exposure to study intervention will be presented for the ES. The number and percentage of participants who received the study intervention will be tabulated by per study intervention group and overall.

6.2. Appendix 2 Electronic Clinical Outcome Assessment (eCOA) Compliance

Not applicable.

6.3. Appendix 3 Data Derivations Rule

6.3.1. Attributing events to vaccine doses

If an event starts on the same day as a study dose, the relative dose will be derived from the additional information provided in the eCRF using the contents of the flag indicating if the event occurred before or after study dose. If 'after study dose' is selected, the relative dose for the event will be the one administered on the start day of the event. If 'before study dose' is selected, the event will not be attributed to the study vaccination.

6.3.2. Study Day and Reference Dates

The onset day for an event (e.g. AE, concomitant medication/vaccination) is the number of days between the study dose and the start date of the event. This is 1 for an event occurring on the same day as a study dose (and reported as starting after study dose).

6.3.3. Assessment Window

For data summaries by visit, the nominal visit description will be used.

Analysis Set / Parameter (if applicable)		Target	Analysis Window		Analysis
Domain			Beginning Timepoint	Ending Timepoint	Timepoint
Immunogenicity	RSV-A & RSV-B Nab and SARs-COV-2 Nab (Co-ad) SARs-COV-2 Nab (control)	Day 1	Day 1	Day 1	VISIT 1
Immunogenicity	RSV-A & RSV-B Nab and SARs-COV-2 Nab (Co-ad & Control)	Day 31	Day 31	Day 42	VISIT 2
Immunogenicity	RSV-A & RSV-B Nab (Control)	Day 61	Day 61	Day 84	VISIT 3

6.3.4. Multiple measurements at One Analysis Time Point

For lab tests on a study day, if more than one assessment is taken on the same day, the test from a central lab will be taken over the test from a local lab. If multiple assessments are taken from the same type of lab, the worst case will be used.

6.3.5. Handling of missing data

6.3.5.1. Dates

Element	Reporting Detail		
General Adverse Events	 Partial dates will be displayed as captured in participant listing displays. However, where necessary, display macros may impute dates as temporary variables for sorting data in listings only. In addition, partial dates may be imputed for 'slotting' data to study phases or for specific analysis purposes as outlined below. Imputed partial dates will not be used to derive study day, time to onset or duration (e.g., time to onset or duration of adverse events), or elapsed time variables (e.g., time since diagnosis). The following standard rules will be applied: A missing day will be replaced by 15 A missing day and month will be replaced by June 30th. Partial dates for AE recorded in the CRF will be imputed using the following 		
	Conventions: Missing start day Missing start day and month	If study intervention start date is missing (i.e. participant did not start study intervention), then set start date = 1st of month. Else if study intervention start date is not missing: If month and year of start date = month and year of study intervention start date, then If stop date contains a full date and stop date is earlier than study intervention start date, then set start date= 1st of month. Else, the flag indicating if the event occurred before or after vaccination will be used to complete the date. If 'after vaccination' is selected, the imputed start date will match the vaccine dose given during that month. If 'before vaccination' is selected, the imputed date will be one day before the last vaccine dose given during that month. Else set start date = 1st of month. If study intervention start date is missing (i.e. participant did not start study intervention), then set start date = January 1. Else if study intervention start date is not missing:	
	Missing end day Missing end day and month Completely missing	 If year of start date = year of study intervention start date, then If stop date contains a full date and stop date is earlier than study intervention start date, then set start date = January 1. Else, the flag indicating if the event occurred before or after vaccination will be used to complete the date. If 'after vaccination' is selected, the imputed start date will match the vaccine dose given during that year. If 'before vaccination' is selected, the imputed date will be one day before the last vaccine dose given during that year. Else set start date = January 1. A '28/29/30/31' will be used for the day (dependent on the month and year) or the study conclusion date whichever comes first. The imputed end date will be the last day of the year (31st of December) or the study conclusion date whichever comes first. No imputation 	
	start/end date	No impatation	

Element	Reporting Detail			
Concomitant	Partial dates for any concomitant medications recorded in the CRF will be imputed			
Medications/Medic		using the following convention:		
al History	Missing start day	If study intervention start date is missing (i.e. participant did not start study intervention), then set start date = 1st of month. Else if study intervention start date is not missing: If month and year of start date = month and year of study intervention start date, then If stop date contains a full date and stop date is earlier than study intervention start date, then set start date= 1st of month. Else, the flag indicating if the event occurred before or after vaccination will be used to complete the date. If 'after vaccination' is selected, the imputed start date will match the vaccine dose given during that year. If 'before vaccination' is selected, the imputed date will be one day before the vaccine dose given during that year. Else set start date = 1st of month.		
	Missing start day and month	If study intervention start date is missing (i.e. participant did not start study intervention), then set start date = January 1. Else if study intervention start date is not missing: If year of start date = year of study intervention start date, then If stop date contains a full date and stop date is earlier than study intervention start date, then set start date = January 1. Else, the flag indicating if the event occurred before or after vaccination will be used to complete the date. If 'after vaccination' is selected, the imputed start date will match the vaccine dose given during that year. If 'before vaccination' is selected, the imputed date will be one day before the vaccine dose given during that year. Else set start date = January 1.		
	Missing end day	A '28/29/30/31' will be used for the day (dependent on the month and year) or the study conclusion date whichever comes first.		
	Missing end day and month	A '31' will be used for the day and 'Dec' will be used for the month or the study conclusion date whichever comes first.		
	Completely missing start/end date	No imputation		

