4.4.1. Adverse Events

An adverse event (AE) is considered study intervention emergent if the AE onset date is on or after study intervention start date. All AE summaries will be based on study intervention emergent events unless otherwise specified. SAE summaries will be based on all SAEs reported regardless of whether they meet the definition of study intervention emergent or not. All AE and SAE summaries will be grouped by SOC, HLT and PT and summarized by study intervention group at time of onset of the AE, unless otherwise specified.

Adverse events will be coded using the standard Medical Dictionary for Regulatory Activity (MedDRA dictionary). The verbatim reports of unsolicited AEs, including SAE and AESI, will be reviewed by a qualified person and the signs and symptoms will be coded according to the MedDRA Dictionary for Adverse Reaction Terminology. Every verbatim term will be matched with the appropriate Preferred Term.

For the summaries of AE and SAE, participants who experience the same AE/SAE (in terms of the MedDRA SOC, HLT and PT) more than once will only be counted once for that event in the number of participants but all occurrences of the same event will be counted in the number of events. Also, in the case of co-administered study interventions, an administration site event recorded for a participant following multiple study interventions will be counted as only one occurrence.

A study intervention-related AE/SAE is defined as an AE/SAE for which the investigator classifies the possible relationship to study intervention as "Yes". A worst-case scenario approach will be taken to handle missing relatedness data, i.e., the summary table will include events with the relationship to study intervention as 'Yes' or missing.

The analyses of unsolicited AEs will include SAEs and AESIs (unless otherwise specified).

The following analysis will be performed:

- Compliance in completing solicited events information will be tabulated after each dose and overall.
- The number and percentage of participants with at least one administration site event (solicited and unsolicited), with at least one systemic event (solicited and unsolicited) and with any AE (solicited and unsolicited) during the 4-day or 30-day follow-up period after vaccination will be tabulated with exact 95% CI for each group, after each dose and overall.

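### For an adverse event with a missing start day, SAP 6.3.5.1 checks the month of one dose only, so a Control event after the RSV dose in that dose's calendar month is usually dated before it

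*SAP*

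**What the plan says.** SAP 6.3.5.1 (Dates) sets the start of an AE whose start day is missing.

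- The flag is reached only through the condition "If month and year of start date = month and year of study intervention start date", and then only if a full stop date does not already place the event before that start date.
- Inside that branch, for an event flagged as after vaccination, "the imputed start date will match the vaccine dose given during that month". For one flagged as before, the date is "one day before the last vaccine dose given during that month".
- In every other month the start is set to the 1st, and the flag is not consulted.

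The rule explains a missing study intervention start date as a participant who never started. SAP 4.4.1 uses the same single date for emergence: an AE is "study intervention emergent if the AE onset date is on or after study intervention start date". Both uses point to one date per participant, the first dose.

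If day and month are both missing, the test is on the year, and for the after-vaccination flag "the imputed start date will match the vaccine dose given during that year". The concomitant-medication rule also refers to the year in the branch where only the day is missing, although that branch tests the month.

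On use, the section says "Imputed partial dates will not be used to derive study day, time to onset or duration", yet it permits imputed dates for placing data in study phases and for particular analyses. SAP 6.3.2 says that onset day "is the number of days between the study dose and the start date of the event". SAP 4.4.1 tabulates unsolicited AEs over 30 days after each dose and overall.

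**The concern.** The Control group has two dose dates and the month test looks at one of them. An AE that follows the RSV dose can therefore receive a start date before that dose, against the site's own record that it began after vaccination. This is a stated rule that yields a wrong date, not a detail left open.

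What is at stake is the Control safety description by dose. Those tables show what follows each vaccine given alone, which is part of a secondary objective. If imputed dates feed them, the shift goes one way, out of the after-RSV table. Co-Ad participants receive both vaccines on one day, so they have no second date to miss.

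**Working it through.** The plan gives no figure on this point, so there is none to reproduce. The rule was applied literally to a calendar.

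**Inputs.** Control dose gap g of 30 to 42 days (protocol visit-interval table for the Control group; SAP Table 2, code 2080). 30-day window: dose day plus 29 days (SAP 4.4.1). Assumptions: first doses spread evenly over a 365-day year; the AE starts k days after the RSV dose, has no start day, and is flagged as after vaccination.

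**Rule in symbols.** First dose s, RSV dose r = s + g, true onset e = r + k. Imputed date = r if e lies in the month of s; otherwise the 1st of the month of e. The AE is pre-dated if the imputed date is earlier than r.

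**Example.** COVID-19 dose 10 April, RSV dose 16 May (g = 36), AE on 18 May recorded only as May. May is not April, so the start becomes 1 May. That is 15 days before the RSV dose and Day 22 after the COVID-19 dose.

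**How often the flag is reached in the RSV-dose month.** Both doses share a calendar month only if the first falls on the 1st of a 31-day month and g is exactly 30. That is 7 start dates a year, and none at 31 days or more. Over all schedules: 7 / (365 × 13) = 7 / 4,745 = 0.15%.

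**Share pre-dated within the RSV-dose month.** The other exception is an RSV dose on the 1st (12 dates a year), where the imputed date equals the dose date.

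- g = 30: (365 − 7 − 12) / 365 = 94.8% of schedules.
- g = 31 to 42: (365 − 12) / 365 = 96.7%.
- Weighted by events: 93.6-93.8% if onset is even over 30 days, 96-97% if onset is on days 0-3.

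**Share of all post-RSV AEs with a missing start day.** An AE in the following month is set to the 1st of that month, which is after the RSV dose, so it is not pre-dated. With even 30-day onset about 52.4% of AEs fall in the RSV-dose month: 0.524 × 0.937 = 49.1%. With onset on days 0-3: 0.951 × 0.965 = 91.8%. The table shows where they land.

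| Gap (days) | Even 0-29: pre-dated | in COVID-19 window / neither | Days 0-3: pre-dated | in COVID-19 window / neither |
|---|---|---|---|---|
| 30 | 49.0% | 49.0% / 0% | 91.3% | 91.3% / 0% |
| 36 | 49.1% | 31.4% / 17.7% | 91.8% | 72.1% / 19.7% |
| 42 | 49.2% | 17.6% / 31.5% | 91.8% | 52.3% / 39.5% |

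If onset is even over 183 days, the pre-dated share is 8%.

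**Year branch.** Both Control doses fall in one calendar year for (365 − 30)/365 = 91.8% at a 30-day gap and (365 − 42)/365 = 88.5% at 42 days. The dose given in that year is then not unique.

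**Effect of the fix.** With each dose's month tested and the flag answered for the RSV dose, even 30-day onset gives 0% pre-dated and 100% in the RSV window at gaps of 30, 36 and 42 days.

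**The case against.** **The use of imputed dates.** The strongest reply is that an imputed date may never reach a by-dose table. The SAP bars such dates from study day and time to onset, and placing an AE in a 30-day window is in substance an onset-day calculation. On that reading no AE moves. This stands as a limit on the consequence: a reader might infer that the Control safety tables will be miscounted, and the documents do not establish that. They do not exclude it either. Placement in study phases is allowed, the flag branch matches an event to a dose, and the SAP gives no other way for a partial-date AE to get its dose.

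**Intent.** The SAP does not formally define the start date, and "one day before the last vaccine dose given during that month" makes practical sense mainly if each dose is tested. That suggests a per-dose intent. The condition as written does not deliver it, so the wording needs correcting either way.

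**Numbers.** No document gives the count of AEs with a missing start day. Diary cards are reviewed at Visits 2 and 3, which should keep it low. Solicited events have their own rule in SAP 6.3.6.6, where a missing start date takes the vaccination date. The 8% to 92% span reflects assumed onset patterns and is not a forecast. All of this stands.

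**Attribution.** A reader might also infer that SAP 6.3.1 leaves the dose unidentified when it relies on "the flag indicating if the event occurred before or after study dose". It does not. For an event starting on a dose day and flagged as after, it names the dose given that day. The flag's reference is unclear only for partial dates.

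**Conclusion.** The point holds as a minor one, limited to AEs with a missing start day. Taking the start date as the first dose, the rule dates a Control AE that follows the RSV dose, in that dose's calendar month, before the dose in about 94-97% of cases. This assumes first-dose dates spread evenly over the year.

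Any effect on tables depends on imputed dates being used to place AEs in a dose or window, which the SAP leaves unclear. If they are, only the descriptive Control by-dose tables of unsolicited AEs change. Overall 30-day counts can also lose an AE when the gap exceeds 30 days. The primary immunogenicity analysis and Co-Ad are not affected. Treatment emergence is also unaffected in these cases, because the 1st of a later month still follows the first dose.

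A separate slip needs no assumption. SAP 4.5.1.2 counts the four-day solicited period as the vaccination day plus six days, while the endpoint in SAP 1.1 counts plus three. It concerns the age-subgroup tables.

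**What to change.** In SAP 6.3.5.1:

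1. Test the AE month (or year, when day and month are both missing) against the month (or year) of each dose, and apply the flag to the matched dose.
2. State, for partial dates, which dose the flag refers to. Otherwise an AE that began before the RSV dose but was flagged as after the COVID-19 dose would be moved onto the RSV dose.
3. State what happens when both Control doses match, using the recorded dose period if the data hold one.
4. State whether imputed dates assign AEs to a dose and a 30-day window.
5. Make the same changes in the concomitant-medication rule, and correct its reference to the year in the missing-day branch.

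In SAP 4.5.1.2, change six further days to three.

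The cost is a short SAP edit and a small change to the date-imputation step. SAP Amendment 2 already revised an imputation rule in Section 6.3.5, so there is precedent. Programming status is not given; if the tables exist, the Control unsolicited AE tables by dose, and any overall 30-day counts that use the imputed dates, need a rerun. Whether the data record which dose the flag refers to must be checked first.
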